adverse event; SARS CoV-2, severe acute respiratory syndrome coronavirus 2; T.Bili, total bilirubin; TSH, thyroid stimulating hormone; WOCBP, women of childbearing potential.

- ^a Participants must be followed for at least 100 days after last dose of study treatment. Follow-up visit 1 (Follow-up 1) = 30 days from the last dose \pm 7 days or coincide with the date of discontinuation (\pm 7 days) if date of discontinuation is greater than 30 days after last dose. Follow-up visit 2 (Follow-up 2) = 100 days (\pm 7 days) from the last dose of study medication.
- ^b From Follow-up 2, all participants will be followed for overall survival status every 12 weeks (\pm 7 days) until the time for the final analysis. Survival status can be ascertained by telephone contact if the participant is unable to return to the site. If new anti-tumor therapy is initiated for either disease recurrence or a secondary malignancy at any time during this period, this and all other pertinent data obtained should be recorded on the appropriate Case Report Form (CRF).
- ^c If participant is unable to perform the patient-reported outcome assessment in person, the EQ-5D-3L and FKSI-19 can be performed via telephone. The same window (\pm 7 days) applies for telephone contacts.

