Adverse Event (AE) Assessment and Serious Adverse Event (SAE) Assessment	Continuously (see Notes)			Participants will be followed for drug-related toxicities until these toxicities resolve, return to baseline, or are deemed irreversible. All adverse events (SAEs and non-serious AEs), including those associated with suspected or confirmed SARS-CoV-2 infection, will be collected continuously during the treatment period and documented for a minimum of 100 days after last dose (Appendix 3).
Review of Concomitant Medications	X	X	X	Record at each visit.
Laboratory Tests	X	X	X	Laboratory tests do not need to be repeated at C1D1 if performed within 14 days prior to first dose. After C1D1, within 72 hours prior to dosing and results should be reviewed prior to administration of each dose of study drug: 
 • CBC w/differential. • Chemistry panel including AST, ALT, ALP, T. Bili, BUN or serum urea level, creatinine, phosphate, Ca, Mg, Na, K, Cl, LDH, glucose, and albumin. • TSH (with reflexive Free T4 and Free T3).

Table 2-2: On-treatment Procedural Outline (CA209914) Part A and Part B

Procedure	Cycle 1 Day 1 (Nivolumab + Ipilimumab)	Cycles 2, 3, 5, 6, 8, 9, 11, & 12 Day 1 ^{a,b} Each Cycle = 2 weeks (Nivolumab alone)	Cycles 4, 7, & 10 Day 1, (Nivolumab + Ipilimumab)	Notes
Pregnancy Test	X	X	X	Within 24 hours prior to the initial administration of study drug, then every 4 weeks, regardless of dose delay. Serum or Urine. WOCBP only.
Pharmacokinetic Samples				
PK Samples	X	X		See Table 9.5-1 . At Cycles 1, 2, 5, 8, & 11.
Immunogenicity blood sample	X	X		See Table 9.5-1 . At Cycles 1, 2, 5, 8, & 11.
Exploratory Biomarker Assessments				
Whole Blood (DNA)	X			Only at baseline.
Serum	X		X	Prior to dosing. At Cycle 1, 4, and 7, and upon occurrence of ≥ Grade 3 non-laboratory drug-related AE and/or lab abnormalities regarded as a drug-related SAE, to be collected when clinically safe and feasible.
ctDNA	X	X (C2D1, C5D1, C9D1 only)		Samples should be collected prior to dosing. Subsequent sample collections will be aligned with tumor assessments performed on Weeks 23, 36, and 52 (± 1 week window). If a tumor assessment is not performed, ctDNA sampling is not required.
Peripheral Blood RNA	X			Prior to dosing at Cycle 1 and upon ≥ Grade 3 non-laboratory drug-related AE and/or laboratory abnormalities regarded as a drug-related SAE, to be collected when clinically safe and feasible.

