Myeloid Derived Suppressor Cells	X		X	Cytochex Tube. Prior to dosing. At Cycle 1 and 7.

Table 2-2: On-treatment Procedural Outline (CA209914) Part A and Part B

Procedure	Cycle 1 Day 1 (Nivolumab + Ipilimumab)	Cycles 2, 3, 5, 6, 8, 9, 11, & 12 Day 1 ^{a,b} Each Cycle = 2 weeks (Nivolumab alone)	Cycles 4, 7, & 10 Day 1, (Nivolumab + Ipilimumab)	Notes
SARS-CoV-2 Serology	X	X (C12D1 only)		Samples should be collected prior to dosing. Serum will be collected at C1D1 and C12D1 for all participants, and approximately 4 weeks after a suspected or confirmed SARS-CoV-2 infection to be used for potential future measurements of anti-SARS-CoV-2 serology (anti-SARS-CoV-2 total or immunoglobulin G (IgG) [see Section 9.8.9]). If a suspected or confirmed SARS-CoV-2 infection occurs within 4 weeks of the C1D1 or C12D1 time point, a single serum sample will be collected to satisfy the requirements for both the C1D1 or C12D1 and approximately 4 week after infection time points.
Efficacy Assessments				
Tumor Assessments	See Notes.			CT/MRI of the chest, abdomen, and pelvis. Assessment should be performed at Weeks 23, 36, and 52 (\pm 1 week) regardless of any dose delays. Use same imaging method as was used at screening/baseline. See Section 9.1.3 for additional details.
Patient-Reported Outcomes				
EQ-5D-3L	X	Cycles 3, 6, 9, and 12		Completed on Day 1 of Cycles 1, 3, 6, 9, and 12 prior to any study-related procedures.
FKSI-19	X ^c	Cycles 3, 6, 9 and 12		Completed on Day 1 of Cycles 1, 3, 6, 9, and 12 prior to any study-related procedures.

Table 2-2: On-treatment Procedural Outline (CA209914) Part A and Part B

Procedure	Cycle 1 Day 1 (Nivolumab + Ipilimumab)	Cycles 2, 3, 5, 6, 8, 9, 11, & 12 Day 1 ^{a,b} Each Cycle = 2 weeks (Nivolumab alone)	Cycles 4, 7, & 10 Day 1, (Nivolumab + Ipilimumab)	Notes
Drug Administration				
Randomize	X			Begins with call to Interactive Response Technology.
Administer nivolumab or placebo	X	X	X	Participants must begin study treatment within 3 calendar days of randomization.
Administer ipilimumab or placebo	X		X	Participants must begin study treatment within 3 calendar days of randomization.

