AE, adverse event; ALP, alkaline phosphatase; ALT, alanine aminotransferase; AST, aspartate aminotransferase; BP, blood pressure; BUN, blood urea nitrogen; C1D1, Cycle 1 Day 1; Ca, calcium; CBC, complete blood count; Cl, chloride; ECOG, Eastern Cooperative Oncology Group; FKSI-19, Functional Assessment of Cancer Therapy - Kidney Symptom Index; HR, heart rate; LDH, lactate dehydrogenase; K, potassium; Mg, magnesium, NA, sodium; SAE, serious adverse event; SARS CoV-2, severe acute respiratory syndrome coronavirus 2; T.Bili, total bilirubin; TSH, thyroid stimulating hormone; WOCBP, women of childbearing potential.

^a If a dose is delayed, the procedures scheduled for that same time point should also be delayed to coincide with when that time point's dosing actually occurs.

^b If all cycles are not given within 36 weeks after the first dose, the participant will discontinue treatment and move to Post-treatment Follow-up.

^c Note: at baseline visit (C1D1) only, Question GP5 on FKSI-19 can be left blank as participant has not yet received treatment.

Table 2-3: Post-treatment Follow-up (CA209914) Part A and Part B

Procedure	Follow-Up Visit 1 and 2 ^a	Survival Follow-Up ^b	Notes
Safety Assessments			
Targeted Physical Examination, Vital Signs, and Performance Status	X		Weight, BP, HR, temperature, and ECOG Performance Status (Appendix 5).
Assessment of Signs and Symptoms	X		

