7.4.1 Dose Delay Criteria for Study Treatment

Regardless of whether or not the event is attributed to Arm A, Arm B, or Arm C, all study drugs must be delayed until criteria to resume treatment ([Section 7.4.2](#)) have been met, given the blinded

nature of this study. Tumor assessments for all participants should continue as per protocol even if dosing is delayed. If one drug is delayed, both study drugs must be delayed.

Study drug administration should be delayed for any of the following:

- Grade 2 non-skin, drug-related AE, with the exception of fatigue
- Grade 2 drug-related creatinine, AST, ALT and/or Total Bilirubin abnormalities
- Grade 3 skin, drug-related AE
- Grade 3 drug-related laboratory abnormality, with the following exceptions:
 - Grade 3 lymphopenia or asymptomatic amylase or lipase does not require dose delay
 - Grade \geq 3 AST, ALT, Total Bilirubin will require dose discontinuation (see [Section 8.1](#))
- Any AE, laboratory abnormality, or intercurrent illness which, in the judgment of the investigator, warrants delaying the dose of study medication.
- SARS-CoV-2 infection (either suspected or confirmed).

Participants who require delay of study drug should be re-evaluated weekly or more frequently if clinically indicated and resume study drug dosing when re-treatment criteria are met. If a participant is delayed beyond 36 weeks of the first dose, treatment will discontinue.

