7.4.2 Criteria to Resume Treatment

All criteria to resume study therapy apply to nivolumab, ipilimumab, and placebo, given the blinded nature of the study. Participants may resume treatment with study drug when the drug-related AE(s) resolve to Grade \leq 1 or baseline value and any systemic corticosteroids have been tapered to \leq 10 mg prednisone equivalent. (See [Section 7.7.3](#) for exception regarding adrenal replacement steroids.)

The following are exceptions to the above:

- Participants may resume treatment in the presence of Grade 2 fatigue
- Participants who have not experienced a Grade 3 drug-related skin AE may resume treatment in the presence of Grade 2 skin toxicity
- For participants with Grade 2 AST, ALT and/or Total Bilirubin Abnormalities, dosing may resume when laboratory values return to baseline and management with corticosteroids, if needed, is complete.
- Drug-related pulmonary toxicity, diarrhea or colitis must have resolved to baseline before treatment is resumed. Participants with persistent Grade 1 pneumonitis after completion of a steroid taper over at least 1 month may be eligible for retreatment if discussed with and approved by BMS Medical Monitor or designee.
- Participants with SARS-CoV-2 infection (either suspected or confirmed) may resume treatment after all of the following: 1) at least 10 days (20 days for severe/critical illness) have passed since symptoms first appeared or positive test result (eg, RT-PCR or viral antigen), 2) resolution of acute symptoms (including at least 24 hours has passed since last fever without fever-reducing medications), 3) evaluation by the Investigator with confirmation that there are

no sequelae that would place the participant at a higher risk of receiving investigational treatment, and 4) consultation by the Medical Monitor. For suspected cases, treatment may also resume if SARS-CoV-2 infection is ruled out and other criteria to resume treatment are met.

If the criteria to resume treatment are met after a delay of Cycle 4, 7, or 10, then both nivolumab and ipilimumab must be resumed on the same day when the cycle is given.

If treatment is delayed > 6 weeks from the previous dose, the participant must be permanently discontinued from study therapy, except as specified in [Section 8.1.1](#).

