10.3.3.3 Outcomes Research Analyses

Descriptive summary statistics of quality of life assessments will be presented at baseline and each on-study time points unless otherwise specified. Mean changes from baseline for each of the 2 assessments and all associated subscores will be calculated for each treatment arm at each on-

study time point. More specifically, summary scores of the FKSI-19 subscale and total scores, the 9-item FKSI-DRS score, and the EQ-5D-3L utility index and VAS at baseline and on-study time points and the 95% CIs will be conducted. For the EQ-5D-3L utility index, the UK preference weightings will be analyzed.⁵⁵ In addition, participant compliance will be described per time point by the proportion of participants who filled out the QoL assessments over the numbers of participants known to be alive and eligible for assessment at these time points.

Additionally, t-tests will be conducted to evaluate the differences between nivolumab combined with ipilimumab versus placebo infusions treatment arms as well as the nivolumab versus placebo infusions treatment arms at each time point, and 95% CIs will also be presented.

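### FKSI-19 and EQ-5D-3L follow the dosing day rather than the calendar, so the by-time-point comparisons with placebo may understate symptom burden, mainly for nivolumab plus ipilimumab

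*Combined protocol and SAP*

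**What the plan says.** Table 2-2 has both questionnaires "Completed on Day 1 of Cycles 1, 3, 6, 9, and 12 prior to any study-related procedures". Footnote a is attached to the column that holds Cycles 3, 6, 9 and 12. It states that after a dose delay "the procedures scheduled for that same time point should also be delayed to coincide with when" that dose is given. Two other rows of the same table are fixed in calendar time: tumor assessments are done "regardless of any dose delays", and pregnancy tests are done before the first dose, "then every 4 weeks, regardless of dose delay". The questionnaire rows carry no such wording.

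Section 7.4.1 delays dosing for, among other events, "Grade 2 non-skin, drug-related AE, with the exception of fatigue". Section 7.4.2 sets the condition for restarting: "Participants may resume treatment with study drug when the drug-related AE(s) resolve to Grade" 1 or lower, or to baseline. Section 8.1.1 keeps safety and laboratory visits going during delays of more than 6 weeks but does not mention questionnaires.

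After treatment stops, Table 2-3 collects both forms at Follow-up 1 (30 days after the last dose), Follow-up 2 (100 days), the first survival visit and every second survival visit after that.

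Section 10.3.3.3 plans mean changes from baseline by arm at each time point. It adds that "t-tests will be conducted to evaluate the differences between nivolumab combined with ipilimumab versus placebo infusions treatment arms", and likewise for nivolumab against placebo, at each time point. It gives no rule for calendar windows and no method for missing forms. Compliance is calculated among participants who are alive and eligible for assessment, and eligibility is not defined.

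**The concern.** The rule that decides when a participant is asked depends on the thing being asked about. The FKSI-19 has a treatment side-effects subscale and a 7-day recall, and the EQ-5D-3L rates current health (Section 9.1.5). A form postponed until an adverse event has subsided will usually miss it. A participant who stops because of an adverse event contributes nothing to the later cycle comparisons.

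If toxicity-related delays and stops are more common on active treatment, the comparison with placebo is made on participants who are, on average, better than their arm was at that calendar time. A finding of little symptom cost against placebo could then be due partly to the timing of the forms. The undefined compliance denominator could hide this: if stopped participants count as not eligible, reported compliance stays high while the arm loses them.

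**Working it through.** The plan gives no SD, meaningful difference, expected completion rate or delay rate for either questionnaire, so it has no figure to reproduce. The check is calendar arithmetic plus an illustrative bound.

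**1. Timing.** Day 1 of cycle c falls in Week 1 + 2(c − 1).
- Cycles 3, 6, 9 and 12 fall in Weeks 5, 11, 17 and 23.
- Cycle 12 is due 2 × 11 = 22 weeks after the first dose. Treatment may run to 36 weeks after the first dose (Section 7.1.1), so the Cycle 12 form can be up to 36 − 22 = 14 weeks late.
- A gap of more than 6 weeks from the previous dose normally ends treatment (Sections 7.4.2 and 8.1.1). One delay therefore adds at most 6 − 2 = 4 weeks, and the full 14 weeks takes at least four delays (14/4 = 3.5) unless a listed exception applies. The extreme will be uncommon; smaller shifts need only one delay.

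**2. What a stopped participant contributes.** Suppose the last dose is Cycle 4 (day 43). Follow-up 1 falls near day 43 + 30 = 73, in Week 11, and Follow-up 2 near day 43 + 100 = 143, in Week 21. By calendar week these forms lie close to the nominal Cycle 6 and Cycle 12 forms. Under the plan's time-point labels they enter neither comparison.

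**3. Illustrative size, stopping only.** If the missing participants are X standard deviations worse than those observed in their arm, the arm difference is understated by

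(share missing in active arm − share missing in placebo) × X.

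The shares below are adverse-event discontinuation rates that the protocol cites from other settings:
- combination: 22% in the phase 3 trial in untreated advanced RCC (Section 3.2.1.3);
- nivolumab: 8% in the phase 3 trial in previously treated advanced RCC (Section 3.2.1.1);
- placebo: 5.6% in the adjuvant sunitinib trial with a positive DFS result (Section 3).

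X is an assumption.

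| Comparison | Excess share | X = 0.25 | X = 0.5 | X = 0.8 |
|---|---|---|---|---|
| Combination, placebo 5.6% | 0.164 | 0.041 | 0.082 | 0.131 |
| Combination, placebo 0% | 0.220 | 0.055 | 0.110 | 0.176 |
| Nivolumab, placebo 5.6% | 0.024 | 0.006 | 0.012 | 0.019 |
| Nivolumab, placebo 0% | 0.080 | 0.020 | 0.040 | 0.064 |

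All entries from X = 0.25 onward are in SD units. If the shares are equal across arms, the shift is zero.

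**4. Scale.** With complete forms, the 95% half-width is 1.96 × √(1/400 + 1/400) = 0.14 SD for Part A. For nivolumab against placebo in Part B it is 1.96 × √(1/400 + 1/200) = 0.17 SD. The combination figures run from about a third of the Part A half-width (0.041/0.14) to slightly above it (0.176/0.14). With placebo stopping at 5.6%, the nivolumab figures are at most 0.019/0.17, about a tenth.

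**5. Delay.** The documents give no delay rate. As an assumption, each 5 percentage points of excess delay would add 0.05 × 0.25 = 0.0125 to 0.05 × 0.8 = 0.04 SD.

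**The case against.** A reader might infer that delayed participants answer only once toxicity is gone. The text does not support that. Grade 1 events may persist at restart. Section 7.4.2 says that "Participants may resume treatment in the presence of Grade 2 fatigue", allows some Grade 2 skin toxicity, and lets controlled endocrinopathies resume after consultation. Fatigue (37%) and pruritus (28%), the two most frequent treatment-related events with the combination in Section 3.2.1.3, do not delay dosing at Grade 2. Some delays have other causes, such as laboratory abnormalities or SARS-CoV-2 infection.

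A reader might also infer that stopped participants are lost to the questionnaires. They are not: they answer at follow-up and may do so by telephone. Those forms are timed from the last dose, however, and Section 10.3.3.3 does not map them onto the cycle time points.

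A third tempting reading is that both active arms are shown to be flattered. The documents give neither direction nor size. The cited rates come from longer treatment, other schedules and mostly advanced disease, and for nivolumab alone they barely differ from placebo. The 22% is also a whole-trial rate, so fewer participants would be missing at early cycles.

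Finally, the questionnaire objectives are exploratory (Table 4-1), adverse events are collected continuously through delays, and DFS and OS are untouched. The detailed statistical analysis plan is not in the supplied text and may contain windowing rules.

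All of this stands as a limit on the claim. None of it removes the link between dosing and asking, or supplies the missing analysis rule.

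**Conclusion.** The concern holds in limited form. On-treatment questionnaires move with dose delays, delayed participants generally answer after recovery to Grade 1 or baseline with the exceptions above, and stopped participants leave the later cycle comparisons. The t-tests may therefore understate symptom burden against placebo.

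The understatement is plausible for nivolumab plus ipilimumab, at about 0.04 to 0.13 SD from stopping alone. It is weak for nivolumab alone, at about 0.006 to 0.019 SD. Both ranges rest on stopping rates borrowed from other settings, an assumed deficit of 0.25 to 0.8 SD, and the assumption that stopped participants are still worse at the missed time points. Delay would add an amount that the documents do not allow anyone to estimate. The consequence is confined to exploratory patient-reported results. It merits correction because the remedy is cheap.

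**What to change.** In Section 10.3.3.3, or in the detailed analysis plan:
- Assign every questionnaire, including Follow-up 1 and 2, to a window by weeks from first dose. Windows centered on Weeks 5, 11, 17 and 23, which are 6 weeks apart, could run 3 weeks either side, with a stated rule for two forms in one window and further windows for later follow-up.
- Compare each active arm with placebo by week in all randomized participants, on or off treatment, for example with a longitudinal model, and add a sensitivity analysis in which missing forms are assumed worse than observed ones.
- Define eligibility so that delayed and stopped participants stay in the compliance denominator, and report completion and delay by arm and week.

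For anyone still on treatment, collect the forms at fixed Weeks 5, 11, 17 and 23 regardless of dose delay or discontinuation, by telephone if needed; Table 2-3 footnote c already allows this in follow-up. Section 10.3.1 indicates that enrollment is complete, so this part may reach few participants.

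The cost is analysis work on data already held, plus possibly a few telephone forms. Some windows will hold two forms or none: the participant in step 2 of the working has none near Week 17. Windowing cannot recover episodes that were never asked about, and active-arm scores may look less favorable.

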3 INTRODUCTION

Renal cell carcinoma (RCC) is the eighth most common cancer in the world with an increasing incidence.¹ In the United States, there were approximately 63,000 new cases in 2015 and almost 14,000 deaths.² There were approximately 84,000 cases of RCC and 35,000 deaths due to kidney cancer in 2012 in the European Union.^{3,4} Despite the earlier detection of smaller kidney tumors, the rate of RCC-related mortality has increased,^{5,6} suggesting that recurrence and advanced disease are responsible for mortality. In this context, optimizing the management of early-stage RCC, as well as advanced RCC, are key priorities in the oncological clinical practice.

When RCC is localized early in the course of the disease, it is well established that radical surgical resection is curative for a proportion of patients however, it is estimated that 20-30% of patients will experience relapse.¹⁶ Most relapses occur within 3 years after surgery, with a median time of 1-2 years however; recurrences have been reported through 30 years.¹⁶ Prognostic factors that have been associated with an increased risk of recurrence include anatomic extent of disease, histopathology, presence of tumor necrosis, and certain biomarkers.⁷ Effective adjuvant therapy, in addition to surgical management, may offer an alternative approach to the standard of care for patients with high risk of recurrence. Investigational research is currently ongoing regarding prognostic factors, time and risk of recurrence, and use of adjuvant therapy in the localized RCC setting.

Several trials have shown no benefit with adjuvant interferon- or interleukin-2-based therapies or a CA-IX antibody. This is in contrast to a number of clinically proven therapies for stage IV RCC.

Additional trials are currently assessing the efficacy of the approved multi-targeted tyrosine kinase inhibitors, including sorafenib (SORCE) and axitinib (ATLAS) (Table 3-1), in the adjuvant setting.

Table 3-1: Clinical Trials Database Listed Large, Multicenter, Placebo-Controlled, Randomized, Double-blind, Adjuvant Clinical Trials in RCC (Completed)

Acronym	Trial No.	Status	Intervention	Funding Body/ Sponsors	Design	Start Date/ Est Complete Date	Stratification	Estimated Enrollment	Outcome Measures
ARISER	NCT00087022	Completed	Girentuximab	Industry; Willex	MC, DB, R, PC	07/2004 10/2012	High-risk patients based on TN stage or Fuhrman grade, ECOG PS = 0 or 1	864	Primary endpoint DFS, not met
ASSURE	NCT0326898	Completed	Sorafenib or Sunitinib	NIH; NCI, ECOG, SWOG, Cancer and Leukemia Group B, NCIC	MC, DB, R, PC	05/2006 04/2016	At least intermediate high-risk UISS, ECOG PS = 0 or 1, clear or non-clear cell RCC	1923	Primary endpoint DFS not met
ATLAS	NCT01599754	Terminated	Axitinib	Industry; SF J Pharma., Pfizer	MC, DB, R, PC	04/2012 05/2019	High-risk UISS, ECOG PS = 0 or 1, predominate clear cell histology	592	OS, DFS, toxicity
PROTECT	NCT01235962	Completed	Pazopanib	Industry; GSK	MC, DB, R, PC	11/2010 04/2017	Modified UISS, Karnofsky performance scale of at least 80, clear cell or predominate clear cell histology	1500	Primary endpoint DFS not met
SORCE	NCT00492258	Completed	Sorafenib	Medical Research Council UK	MC, DB, R, PC	05/2007 2013	Intermediate- and high-risk SSIGN, ECOG PS = 0 or 1, clear or non-clear cell RCC	1656	OS, DFS, toxicity, QoL
SWOG-S0931	NCT01120249	Active, not recruiting	Everolimus	NIH, SWOG, NCI	MC, DB, R, PC	04/2011	Pathological high or very high risk, no further details available, ECOG PS = 0 or 1	1218	RFS, OS toxicity

Table 3-1: Clinical Trials Database Listed Large, Multicenter, Placebo-Controlled, Randomized, Double-blind, Adjuvant Clinical Trials in RCC (Completed)

Acronym	Trial No.	Status	Intervention	Funding Body/ Sponsors	Design	Start Date/ Est Complete Date	Stratification	Estimated Enrollment	Outcome Measures
S-TRAC	NCT003 75674	Completed	Sunitinib	Industry, Pfizer	PC, DB, R, DB	07/2007 06/2017	High-risk UISS, ECOG PS = 0-2, predominate clear cell histology	720	Primary endpoint DFS met per IRC not met per investigator. OS (immature)

ARISER, Adjuvant Rencarex Immunotherapy Phase III trial to Study Efficacy in non-metastatic RCC⁸; ASSURE, Adjuvant Sorafenib or Sunitinib for Unfavorable Renal Carcinoma; ATLAS, Adjuvant Axitinib⁹ Treatment of Renal Cancer: A Randomized Double-blind Phase 3 Study of Adjuvant Axitinib v Placebo in Subjects at High Risk of Recurrent RCC; PROTECT, a Randomized, Double-blind, Placebo-controlled Phase III Study to Evaluate the Efficacy and Safety of Pazopanib as Adjuvant Therapy for Subjects with Localized or Locally Advanced RCC Following Nephrectomy; SORCE, a Phase III Randomized, Double-blind Study Comparing Sorafenib with Placebo in Patients with Resected Primary Renal Cell Carcinoma at High or Intermediate Risk of Recurrence; S-TRAC, Sunitinib Treatment of Renal Adjuvant Cancer: A Randomized Double-blind Phase 3 Study of Adjuvant Sunitinib v Placebo in Subjects at High Risk of Recurrent RCC¹⁰; SWOG-S0931, EVEREST, EVERolimus for Renal Cancer Ensuring Surgical Therapy, a Phase III Study.

DB, Double-blind; ECOG, Eastern Cooperative Group; DFS, Disease-free survival; PS, performance score; MC, multicenter; NCI, National Cancer Institute; NIH, National Institute of Health; OL, open-label; OS, overall survival; PC, placebo-controlled; QoL, quality of life; SWOG, Southwest Oncology Group; R, randomized; TN, tumor, node; UISS, UCLA Integrated Staging System

The first trial to report results, ECOG 2805 (ASSURE), revealed no benefit in disease-free survival (DFS) after 1 year of adjuvant sunitinib or sorafenib versus placebo.¹¹ Median DFS was 5.8 years (IQR, 1.6–8.2) for sunitinib (hazard ratio [HR] 1.02, 97.5% CI 0.85–1.23, P = 0.8038), 6.1 years (IQR, 1.7–not estimable [NE]) for sorafenib (HR 0.97, 97.5% CI 0.80–1.17, P=0.7184), and 6.6 years (IQR, 1.5–NE) for placebo. The most common Grade 3 or worse AEs were hypertension (105 [17%] participants on sunitinib and 102 [16%] participants on sorafenib), hand-foot syndrome (94 [15%] participants on sunitinib and 208 [33%] participants on sorafenib), rash (15 [2%] participants on sunitinib and 95 [15%] participants on sorafenib), and fatigue (110 [18%] participants on sunitinib and 44 [7%] participants on sorafenib). Reduced doses of sunitinib still resulted in high toxicity.

In the Phase III PROTECT trial, 1538 participants with completely resected RCC were randomly assigned to pazopanib or placebo for 1 year. The starting dose of pazopanib was reduced from 800 to 600 mg daily, after enrollment of 403 participants, due to high rates of treatment discontinuations due to excess risk of hepatotoxicity. After median follow-up of approximately 60 months, DFS for those treated with 600 mg/day dosing was not statistically different between pazopanib and placebo (67 versus 64 percent three-year DFS, HR 0.94, 95% CI 0.77-1.14). However, DFS was improved for those assigned to 800 mg/day dosing (66 versus 56 percent, HR 0.66, 95% CI 0.49-0.90). Overall survival, a secondary endpoint, was immature.¹²

In a Phase III randomized, double-blind, placebo-controlled trial (ATLAS) conducted in 724 participants with localized RCC status postnephrectomy, axitinib 5 mg oral twice daily, failed to demonstrate a DFS advantage in the total study population. There was no significant difference in DFS per independent review committee assessment in the intention-to-treat population (HR 0.870, 95% CI 0.660–1.147; p 0.3211) or per investigator assessment (HR 0.776, 95% CI 0.599–1.005; P = 0.0536). Overall survival data were not mature. Grade 3 or greater toxicities were more frequent in the axitinib arm (61 versus 30 percent).¹³

Another large Phase III trial, ARISER, a double-blind, placebo-controlled study, evaluated girentuximab (an antibody targeting carbonic anhydrase IX). Co-primary endpoints were DFS and OS assessed by independent radiologic review. No statistically significant DFS (HR = 0.97; 95% CI 0.79–1.18) or OS (HR = 0.99; 95% CI 0.74–1.32) benefit was observed.¹⁴

In SORCE, a Phase III study comparing sorafenib 400 mg twice daily for 3 years, sorafenib 400 mg twice daily for 1 year followed by placebo for 2 years, and placebo for 3 years. Participants were randomized in a 3:3:2 fashion. This study targeted intermediate- or high-risk disease by Leibovich score and allows both clear cell and non-clear cell histologies. The initial sorafenib dose was 400 mg twice per day orally, amended during trial recruitment to a reduced starting dose of 400 mg daily. The primary outcome was investigator-reported DFS. There were no differences in DFS or OS for all randomized participants, high-risk participants only, and participants with only clear cell RCC. Median DFS was not reached for three years of sorafenib or for placebo (HR= 1.01, 95% CI 0.82 -1.23, P = 0.946). The mean DFS was 6.81 years for three years of sorafenib and 6.82 years for placebo, a difference of 0.01 (95% CI 0.49 – 0.48, P = 0.99).¹⁵

Recently, the S-TRAC study was reported to have met its primary endpoint of improved DFS by blinded independent central review (BICR) for sunitinib vs placebo. The population targeted in the study was predominantly clear cell and had a diagnosis of locoregional RCC (tumor stage 3 or higher, regional lymph-node metastasis or both) on the basis of modified UISS criteria. The median DFS was 6.8 years (95% CI, 5.8 to NR) vs 5.6 years (95% CI, 3.8 to 6.6), (HR = 0.76, 95% CI, 0.59-0.98, P = 0.03). Of note, investigator-assessed DFS did not show any statistical difference between sunitinib and placebo. Overall survival (OS) data were not mature at the time of data cutoff. Dose reductions because of AEs were more frequent in the sunitinib group than in the placebo group (34.3% vs 2%), as were dose interruptions (46.4% vs 13.2%) and discontinuations (28.1% vs 5.6%). Grade 3 or 4 AEs were more frequent in the sunitinib group (48.4% for Grade 3 events and 12.1% for Grade 4 events) than in the placebo group (15.8% and 3.6%, respectively). There was a similar incidence of serious adverse events (SAEs) in the 2 groups (21.9% for sunitinib vs 17.1% for placebo). No deaths were attributed to toxic effects. From a quality of life prospective, participants in the sunitinib arm had lower scores (EQ-5D and QLC-C30) than the placebo group, reaching clinically significant differences for diarrhea and loss of appetite.¹⁰

Based on the above results, sunitinib (50 mg daily 4 weeks on, 2 weeks off, for 1 year) was approved in the United States as adjuvant therapy following nephrectomy for participants at high risk of relapse. Although improved DFS findings per BICR were noted in the S-TRAC study, there was an absence of DFS improvement based on investigator assessment, immature OS finding, a need for frequent dose adjustments, and interruptions to manage sunitinib-related toxicities, and an overall decrease in quality of life of participants on sunitinib. National Cancer Comprehensive Network (NCCN) guidelines have been updated and indicate for RCC clear cell histology and high risk; clinical trial (preferred) or surveillance or adjuvant sunitinib (category 2B).¹⁶

In conclusion, at this time, surgery for primary tumors remains the best chance to cure patients with localized RCC. However, survival rates in higher risk patients remain poor, and novel therapeutic approaches are needed to improve prognosis in these patients.

